C. 7 High-Intensity Interval Training (HIIT). HIIT participants will complete three leg cycle ergometer bouts weekly. During the first two weeks, the participants will complete 13, 30-second high intensity exercise intervals at a wattage prescribed to elicit 67% of PPO. Each 30-second exercise interval will be followed by a 1-minute active recovery interval at 30% of PPO. Each week, prescribed wattage will be increased by 4% of PPO. Thus, in the final week, the training intensity will be at 87% of PPO (See table 1 for training example). At the start of the third week, the exercise duration will be increased. Specifically, the 13, 30-second-high intensity intervals will increase to 10, 60-second high intensity intervals. All sessions will start with a three-minute warm-up and end with a two-minute cool-down on the cycle ergometer. In sedentary panic disorder patients, a 12 day HIIT training intervention of similar initial exercise intensity was well tolerated and showed rapid reductions in symptoms (Plag, Ergec, Fydrich, & Strohle, 2019). During the exercise sessions, ratings of perceived exertion, quadriceps pain, and heart rate during the exercise sessions will be assessed 0, 5, 10, 15, 20 minutes into the HIIT.

C.7 Waitlist Control (WL). Participants randomly assigned to the waitlist will visit the laboratory in order to complete the baseline, bi-monthly assessments and post-assessments. They will be asked to maintain their current lifestyle. They will be given the option to receive a six-week supervised HIIT training program after the waitlist participation.

D. Primary Outcome Measures for the Specific Aim

D.1 Specific Aim 1. Evaluate the impact of six-weeks of high intensity interval training on sleep quality and whether the effect is accounted for by the change in vagal tone.

Pittsburgh Sleep Quality Index-(PSQI): The PSQI is the gold standard measure of self-reported sleep quality. It consists of 19 items. Scores range from 0-21, higher scores indicate poorer sleep quality. A global score ≥ 5 indicates poor sleep quality with a sensitivity of 0.90 and specificity of 0.87 compared to polysomnographically determined poor sleep (Buysse et al., 1989). The PSQI instructions will be modified to better assess rapid changes in usual sleep habits (last two weeks rather than the past month).

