Cardiac Vagal Tone: Each participant will place a bioharness monitor on in a private room. The R-R waveform will be sampled at 1000 hertz. Fast Fourier transformation will be applied, spectral power will be determined, and the average of the frequency domain will be calculated using Kubios analysis software (Tarvainen, Niskanen, Lipponen, Ranta-aho, & Karjalainen, 2014). After the frequency units from the heart cycles are converted to hertz, the vagal tone (high frequency band; 0.15-0.5 Hz), sympathetic tone (low frequency band; 0.05-0.15 Hz) and total power (0.017-0.5 Hz) will be calculated. The *apriori* focus is on changes in vagal tone.

Arithmetic Stress Task: Vagal tone will be measured at rest and during a stressor involving math calculations. Serial subtraction will be administered by a research team member dressed in white lab coat, with a clip board and pen for making notes. The team member will correct participants every time an incorrect answer is given and prompt participants to increase their pace every 15 seconds. Serial subtraction will involve sequentially subtracting 13 from a 4-digit number, and if an incorrect response is given, they will be asked to start over. The subtraction task will last a total of 10 minutes.

D.1.1 Expected Results. Based on our review of exercise training studies (McGranahan & O'Connor, 2021), we hypothesize HIIT to result in a clinically meaningful, moderate-sized or greater improvement in sleep quality. It is hypothesized that exercise-training induced changes in vagal tone will mediate the improvements in sleep quality. We do not expect improvements for sleep quality or vagal tone in the control group.

D.1.2 Statistical Power. A sample of 60 total participants will provide statistical power of 80%, at an alpha of 0.05. Assuming a moderate-sized interaction effect of 0.47 on sleep quality and a correlation of 0.85 between repeated measurements, the calculated sample size is 30 per group. Meta-analyses of participant drop out in exercise training trials shows that an average of 20% in the exercise groups and 15% in the control groups drop out (Kelley & Kelley, 2013). Using 20% attrition, recruiting 36 per group will result in 30 completers per group. The short-term (six-week) training duration should result in less than 20% compared to the meta-analysis which included primarily longer-term trials.

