D.1.3 Statistical Analysis. ANOVA will examine the effect of exercise training on sleep quality. Mediation of the effect by the change in vagal tone will be tested by adding the variable as a covariate to the model. A change in the significance of the f-value would indicate significant mediation (Baron & Kenny, 1986; Fiske, Kenny, & Taylor, 1982). To quantify the effect size exercise training has on sleep quality at weeks 2, 4, and 6 and vagal tone at baseline and post, Hedges' d will be calculated.

D. 2.0 Specific Aim 2. Evaluate the impact of six-weeks of high intensity interval training on sleep quality, statistically testing for the effect of the change in trait anxiety and hyperarousal symptoms.

State and Trait Anxiety Inventory: Trait anxiety will be used and is reduced after exercise training (J. W. Whitworth et al., 2019a).

The Posttraumatic Diagnostic Scale-5 (PDS-5): Hyperarousal symptoms will be measured using the hyperarousal subscale of the Posttraumatic Diagnostic Scale-5 (PDS-5). The full 24-item scale also will be used as part of the inclusion criteria to assess PTSD symptoms in the past month based on the diagnostic criteria for the DMS-5. The full PDS-5 assesses trauma history, symptom onset, and index of trauma. Internal consistency of the full PDS-5 and the hyperarousal subscale ≥ 0.90 .

D.2.1 Expected Results. Hyperarousal and anxiety symptoms are expected to decrease after HIIT and be correlated with improvements in sleep quality.

D.2.2 Statistical Analysis. A time-varying covariate analysis will determine if sleep quality changes are explained by the change in trait anxiety or hyperarousal at weeks 2-, 4-, or 6- of the intervention (Winer, 1991). To quantify the effect size exercise training has on PTSD symptoms and anxiety at weeks 2, 4, and 6, Hedges' d will be calculated.

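### Aim 2 uses the unmodified PDS-5 hyperarousal subscale to explain PSQI change and does not guard against a sleep item that the two instruments might share

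*Combined protocol and SAP*

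**What the plan says.** The sleep outcome is the PSQI, which section D.1 introduces as follows: "The PSQI is the gold standard measure of self-reported sleep quality".

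For Aim 2, section D.2.0 gives the hyperarousal measure: "Hyperarousal symptoms will be measured using the hyperarousal subscale of the Posttraumatic Diagnostic Scale-5 (PDS-5". The full PDS-5 is also used at entry to "assess PTSD symptoms in the past month based on the diagnostic criteria for the DMS-5" (the last word is evidently DSM-5), with a total above 27 required in C.3. On reliability, D.2.0 states: "Internal consistency of the full PDS-5 and the hyperarousal subscale ≥ 0.90".

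Section D.2.2 gives the covariate its role: "A time-varying covariate analysis will determine if sleep quality changes are explained by the change in trait anxiety or hyperarousal". Section D.2.1 predicts the result: "Hyperarousal and anxiety symptoms are expected to decrease after HIIT and be correlated with improvements in sleep quality".

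The documents do not list the subscale's items, say how many there are, or reproduce the diagnostic criteria. They exclude no item, define no sleep-free score and plan no sensitivity analysis for overlap with the PSQI.

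**The concern.** A covariate can explain an outcome in a useful sense only if it measures something else. If one hyperarousal item asks about sleep, a woman who only sleeps better scores lower on both instruments. The covariate test in D.2.2 and the correlation in D.2.1 would then tend to be positive even if training changed no other arousal symptom. Part of the evidence that reduced hyperarousal goes with better sleep would be sleep measured twice.

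This problem concerns shared content. Aligning the recall periods of the two instruments, or settling which change comes first, would not remove it.

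**Working it through.** The plan gives no figure on this point, so there is nothing to reproduce. The calculation below is an illustration.

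**From the documents**
- 60 completers, from D.1.2: "A sample of 60 total participants will provide statistical power of 80%, at an alpha of 0.05".
- Four visits: baseline and weeks 2, 4 and 6, the time points in D.1.3 and D.2.2.
- Subscale internal consistency of at least 0.90 (D.2.0).

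**Assumed**
- Six equal-variance items, one of them on sleep.
- The other five are unrelated to the PSQI and to the sleep item, and correlate ρ with each other.
- The sleep item's within-person correlation with the PSQI, r, is 0.3, 0.5 or 0.7.
- The model has person fixed effects and visit and group-by-visit terms.

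**Step 1: variance and reliability.** The six-item sum has variance V = 6 + 20ρ, and alpha = (6/5)(1 − 6/V).
- ρ = 0.2: V = 10, alpha = 0.48.
- ρ = 0.4: V = 14, alpha = 0.69.
- ρ = 0.9: V = 24, alpha = 0.90, which matches the documented value.

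**Step 2: correlation from overlap alone.** r_sub = r/√V, and the share of within-person PSQI variance explained is r²/V. The smallest value is 0.09/24 = 0.4% and the largest is 0.49/10 = 4.9%.

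**Step 3: how often the covariate is significant.** There are 60 × 4 = 240 observations. Removing 60 person, 3 visit and 3 group-by-visit terms leaves 174. Approximately, λ = r_sub·√174/√(1 − r_sub²), and the rejection rate is P(Z > 1.96 − λ) plus a negligible lower tail.
- r = 0.5, ρ = 0.2: r_sub = 0.158, λ = 2.11, rate 56%.
- r = 0.5, ρ = 0.9: r_sub = 0.102, λ = 1.35, rate 27%.

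| r | Simulated, ρ = 0.2-0.4 | Formula, ρ = 0.2-0.4 | Simulated, ρ = 0.9 | Formula, ρ = 0.9 | Simulated, sleep item removed |
|---|---|---|---|---|---|
| 0.3 | 19-24% | 19-24% | 12% | 13% | about 5% |
| 0.5 | 44-57% | 43-56% | 27% | 27% | about 5% |
| 0.7 | 69-85% | 71-85% | 46% | 48% | about 5% |

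Repeat simulations of 2,000 trials per cell agree within a few percentage points.

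**Step 4: how much of the training effect is absorbed.** This uses a simpler model, PSQI change on group plus covariate change. The group effect is in SD units of change and comes from D.1.2: "Assuming a moderate-sized interaction effect of 0.47 on sleep quality and a correlation of 0.85 between repeated measurements". That gives 0.47/√(2 × (1 − 0.85)) = 0.858. Item changes are taken as independent, with r = 0.5 to 0.7. Adjusting for the full subscale shrinks the effect by about 4-8% with six items and 6-12% with four. Adjusting for the sleep-free score shrinks it by about 0%.

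**The case against.** The strongest objection is that the premise is not in the documents. They name the subscale and tie the PDS-5 to the DSM-5 criteria, but print neither items nor criteria. A reader might infer that the subscale does contain a sleep item, and that hyperarousal will be credited with the PSQI change by construction. The documents do not support that inference. This part of the objection stands, and the point is therefore conditional on checking the form.

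The second objection concerns size. Inter-item correlations of 0.2-0.4 imply an alpha of 0.48-0.69, below the documented 0.90. Matching 0.90 brings the rates down to about 12%, 27% and 46%. This also stands, which is why the full range is shown. The documented value may describe differences between women, whereas the simulation concerns changes within women, so it does not settle which end applies. The 5% rate after removing the item follows from assuming that the other items are unrelated to the PSQI. It shows that the test is then calibrated, and does not predict what this trial would find.

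Third, D.2.2 asks what is explained, and a rejection rate is not a share explained. The shares are small: about 0.4-5% of within-person variance, and about 4-12% of the training effect in the simpler model. That rules out wholesale false attribution. It does not rescue the covariate test or the D.2.1 correlation, which could still be positive for the wrong reason.

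Finally, keeping the full subscale as the main covariate, with the sleep-free score as sensitivity analysis, would show the same two results and preserve comparability. That is a reasonable alternative. The sleep-free score is preferred as the main covariate because it addresses the D.2.2 question without shared content.

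**Conclusion.** The point holds conditionally. The plan uses the whole subscale to explain PSQI change and has no safeguard against shared sleep content. If one of six items concerns sleep and the others are unrelated to the PSQI, the covariate is significant in about 12-24%, 27-57% and 46-85% of trials at item correlations of 0.3, 0.5 and 0.7. The lower ends correspond to an alpha of 0.90. The item count, the presence of a sleep item and the correlations are all assumptions.

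A reader might also infer that Aim 2 as a whole cannot be interpreted. That goes too far: the attribution due to overlap is partial, and the trait-anxiety covariate is not in question. The Aim 1 analysis of the training effect on the PSQI is unaffected. This is a cheap improvement.

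**What to change.** First, check the items on the PDS-5 form in use and list the hyperarousal items in D.2.0.

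Then, in D.2.0 and D.2.2, define the Aim 2 hyperarousal covariate as the mean of the hyperarousal items, leaving out any that asks about sleep. Use the same score for the D.2.1 correlation. Report the full subscale alongside as a sensitivity analysis. Leave the PDS-5 total used for screening (above 27) as it is. If no item concerns sleep, the wording changes nothing.

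The cost is about one sentence of analysis text and no new data. The score becomes slightly shorter and is not directly comparable with published subscale values. The loss of reliability is small. Starting from 0.90 with roughly equivalent items, the Spearman-Brown formula gives (5/6 × 0.90)/(1 − 0.90/6) = 0.88 when one of six items is dropped, and (3/4 × 0.90)/(1 − 0.90/4) = 0.87 when one of four is dropped.

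### The Aim 2 analysis does not tie its 'explained by' conclusion to the HIIT effect, so symptoms and sleep merely moving together could be reported as explaining it

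*Combined protocol and SAP*

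**What the plan says.** D.2.0 sets the aim: "Evaluate the impact of six-weeks of high intensity interval training on sleep quality, statistically testing for the effect of the change in trait anxiety". Hyperarousal is named there as the second symptom. The object is therefore the effect of training, with symptom change as a candidate account of it.

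D.2.1 predicts that hyperarousal and anxiety will fall after HIIT and "be correlated with improvements in sleep quality". It gives no size for that correlation.

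D.2.2 gives the analysis: "A time-varying covariate analysis will determine if sleep quality changes are explained by the change in trait anxiety or hyperarousal". The symptom change is taken at week 2, 4 or 6. The section names no model, arm term or arm-by-time term, and no criterion for 'explained'. It also plans Hedges' d for the training effect on PTSD symptoms and anxiety, but does not connect that figure to the conclusion.

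D.1.3 does state a criterion, for vagal tone under Aim 1: "A change in the significance of the f-value would indicate significant mediation". D.2.2 neither repeats it nor rules it out.

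**The concern.** To say that a symptom explains the HIIT effect on sleep, two links are needed: HIIT must move the symptom relative to waitlist, and the symptom must go with sleep within arm. D.2.2 as worded needs only the second. A woman may sleep worse in fortnights when she is more anxious, whichever arm she is in. A time-varying covariate picks that up even if training does nothing, or improves sleep by some other route. Separating within-woman from between-woman variation does not cure this. A clean within-woman coefficient shows that symptoms and sleep move together, not that symptom change carries the training effect.

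At stake is the inference for one of the trial's two aims. Depending on how the analyst fills the gap, the same data could support a claim about how HIIT works or fail to.

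**Working it through.** **Inputs from the plan.** D.1.2: "A sample of 60 total participants will provide statistical power of 80%, at an alpha of 0.05", that is 30 per arm; and "Assuming a moderate-sized interaction effect of 0.47 on sleep quality and a correlation of 0.85 between repeated measurements". Symptom visits: baseline and weeks 2, 4 and 6 (C.6, D.2.2). Sleep visits: baseline and post only in C.6, but weeks 2, 4 and 6 in D.1.3. Both cases are run.

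**Assumptions.** The within-woman symptom-sleep correlation r is not in the documents, so it is varied. The 0.85 and 0.47 are stated for sleep only and are borrowed for the symptom. Tests are two-sided at 0.05. The correlation between the two symptoms is taken as 0.5.

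**The plan's own figure.** D.1.2 gives 30 per group for Aim 1; Aim 2 has none. With a change-score SD of √(2(1 − 0.85)) = 0.548, n = 2 × (1.96 + 0.84)² × 0.30 / 0.47² ≈ 21.3, or 22 per group with the t correction (power 91% at 30). The closest variant tried, a four-visit interaction with the effect building linearly to 0.47, needs 28 per group. The 30 was not reproduced, but nothing below depends on it.

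**Covariate test with inert HIIT.** After removing woman and arm-by-visit effects, residual df ν = (60 − 2) × 3 − 1 = 173 for four visits, and 60 − 2 − 1 = 57 for a single change score. By Fisher's z, P(significant) ≈ Φ(atanh(r) × √(ν − 1) − 1.96).

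- Four visits, √172 = 13.11: r = 0.1 gives Φ(−0.64) = 26%; 0.2 gives Φ(0.70) = 76%; 0.3 gives Φ(2.10) = 98%.
- Two visits, √56 = 7.48: Φ(−1.21) = 11%; Φ(−0.44) = 33%; Φ(0.36) = 64%.

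Simulation (10,000 trials per row) agrees:

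| r | Four visits, one symptom | Four visits, either of two symptoms | Baseline and week 6, one symptom | F-value rule of D.1.3, four visits |
|---|---|---|---|---|
| 0 | 5% | 9% | 5% | 0.4% |
| 0.1 | 25% | 39% | 12% | 0.5% |
| 0.2 | 76% | 89% | 33% | 1.0% |
| 0.3 | 98% | 99.7% | 65% | 1.4% |
| 0.4 | 100% | 100% | 89% | 2.0% |

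At r = 0.5 the F-value rule reaches 2.5%. The covariate test passes 50% at r ≈ tanh(1.96/13.11) ≈ 0.15 with four visits and tanh(1.96/7.48) ≈ 0.26 with two.

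**HIIT improves sleep by 0.47 SD but leaves the symptom unchanged.** The true indirect effect is zero, yet the covariate is significant in 27%, 76% and 98% of trials at r = 0.1, 0.2 and 0.3 (four visits).

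**A true route: HIIT lowers both sleep score and symptom by 0.47 SD.** At r = 0.2, 0.3 and 0.4 the F-value rule declares mediation in only about 22%, 31% and 42% of trials. Requiring both the arm difference in symptom change and the within-arm slope to be significant, using all visits for the slope, succeeds in about 69%, 89% and 90%, with about 4–5% false claims when HIIT is inert. A bootstrapped product on week-6 change alone succeeds in about 37–82% over the same range.

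**The case against.** **No criterion is stated.** A reader might infer that D.2.2 adopts covariate significance as its rule. It does not; that is one reading. D.2.0 opens with the impact of HIIT, and D.1.3 shows the plan using a covariate to see whether the training F-value changes. Carried over, that rule makes few false claims. This stands, and it limits the finding to a missing link between conclusion and treatment effect. It does not rescue the plan: D.2.2 uses a differently named method with its own reference, and the F-value rule misses most true routes at the planned size.

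**Other planned outputs carry the arm comparison.** D.1.3 tests HIIT on sleep, and Hedges' d describes the training effect on symptoms. If the covariate result is read only after a significant arm-by-time effect on sleep, false claims with inert HIIT fall to 1.2%, 3.6% and 5.0% at r = 0.1, 0.2 and 0.3. So it would go too far to say that a positive Aim 2 result tells nothing about HIIT. But when HIIT helps sleep by another route, the same pair of tests is met in 22%, 63% and 82% of trials, and no written rule uses Hedges' d to stop the claim.

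**r is unknown and may be small.** With repeat correlation 0.85, only 15% of variance is within woman. If both measures had reliability 0.90 (D.2.0 gives at least 0.90 internal consistency for the PDS-5 only) and independent errors, 0.10 of that 0.15 would be error, and an observed r of 0.2 would need a true r of 0.2 × 0.15/0.05 = 0.6. At reliability 0.95 it would need 0.3. Recall windows also differ: two weeks for the PSQI, a month for the PDS-5. Correlated errors would push r up. The range is open, which is why r = 0.1 is shown.

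**Conclusion.** The concern holds in conditional form. D.2.2 lets 'explained by' be concluded without a HIIT effect on the symptom and without any shrinkage of the HIIT effect on sleep. That defect is in the wording and does not depend on r.

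Its size does. On the coefficient reading, inert HIIT yields a positive result in about 25–98% of trials for r of 0.1–0.3 with four visits, and 12–65% with sleep at baseline and week 6 only. A reader might go further and expect a false explanation in most trials, or in nearly every data set. The documents do not support that: they give no r, conflict on the sleep visits and state no criterion. With one symptom, 'most' needs r above about 0.15 (four visits) or 0.26 (two visits).

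On the F-value reading the problem is the reverse: false claims of about 2.5% or less, but a 0.47 SD route found in only about 22–42% of trials at r of 0.2–0.4. The sponsor should correct this before analysis. Confidence is medium, because the intended criterion is unknown.

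**What to change.** In D.2.2, conclude that trait anxiety (and, separately, hyperarousal) explains the HIIT effect on sleep only if the indirect effect differs from zero. Define it at one prespecified week, week 6, as the baseline-adjusted HIIT-minus-waitlist difference in symptom change times the within-arm slope of sleep on symptom. Estimate the slope from all visits at which both are measured, and give a 95% interval by bootstrapping women within arm.

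Report the HIIT effect on PSQI with and without the symptom in the model. Report the time-varying coefficient as an association only. Restate the D.2.1 prediction as an indirect effect. Reconcile C.6 with D.1.3 on when sleep is measured, since this decides how much data the slope has.

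Cost: wording in D.2.1 and D.2.2 and a short bootstrap; no new data or participants. The claim becomes harder to reach. For a 0.47 SD effect on both measures and r of 0.2–0.4, expect roughly 69–90% success if the slope can use all visits (the figure for the joint-significance rule), and about 37–82% if only week-6 change is available. The slope is not randomised, so even a clear indirect effect remains open to confounding between symptom and sleep.
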